- [Planned Emergency Research Involving Waiver of Informed Consent*](#)

*For Planned Emergency Research Involving Waiver of Informed Consent, also go to the E-IRB Application Informed Consent section, checkmark and complete "Request for Waiver of Informed Consent Process"

- [Use, storage and disposal of radioactive material and radiation producing devices](#)

64473
CLOSED

FUNDING/SUPPORT

0 unresolved
comment(s)

If the research is being submitted to, supported by, or conducted in cooperation with an external or internal agency or funding program, indicate below all the categories that apply. [?](#)

 Not applicable

Check All That Apply

- Grant application pending
- (HHS) Dept. of Health & Human Services
 - (NIH) National Institutes of Health
 - (CDC) Centers for Disease Control & Prevention
 - (HRSA) Health Resources and Services Administration
 - (SAMHSA) Substance Abuse and Mental Health Services Administration
- (DoJ) Department of Justice or Bureau of Prisons
- (DoE) Department of Energy
- (EPA) Environmental Protection Agency
- Federal Agencies Other Than Those Listed Here
- Industry (Other than Pharmaceutical Companies)
- Internal Grant Program w/ proposal
- Internal Grant Program w/o proposal
- National Science Foundation
- Other Institutions of Higher Education
- Pharmaceutical Company
- Private Foundation/Association
- U.S. Department of Education
- State

Other:

Specify the funding source and/or cooperating organization(s) (e.g., National Cancer Institute, Ford Foundation, Eli Lilly & Company, South Western Oncology Group, Bureau of Prisons, etc.):

 NA

Click applicable listing(s) for additional requirements and information:

- [\(HHS\) Dept. of Health & Human Services](#)
- [\(NIH\) National Institutes of Health](#)
- [\(CDC\) Centers for Disease Control & Prevention](#)
- [\(HRSA\) Health Resources & Services Administration](#)
- [\(SAMHSA\) Substance Abuse & Mental Health Services Administration](#)
- Industry (Other than Pharmaceutical Companies) [\[IRB Fee Info\]](#)
- [National Science Foundation](#)
- [\(DoEd\) U.S. Department of Education](#)
- [\(DoJ\) Department of Justice or Bureau of Prisons](#)
- [\(DoE\) Department of Energy Summary and Department of Energy Identifiable Information Compliance Checklist](#)
- [\(EPA\) Environmental Protection Agency](#)

Add Related Grants

If applicable, please search for and select the OSPA Account number or Electronic Internal Approval Form (eIAF) # (notif #) associated with this IRB application using the "Add Related Grants" button.
If required by your funding agency, upload your grant using the "Grant/Contract Attachments" button.

The research involves use of Department of Defense (DoD) funding, military personnel, DoD facilities, or other
(See [DoD SOP](#) and [DoD Summary](#) for details)

Yes No

Using the "attachments" button (below), attach applicable materials addressing the specific processes described in the DoD SOP.

[DOD SOP Attachments](#)

Additional Certification: (If your project is federally funded, your funding agency may request an Assurance/ Certification/Declaration of Exemption form.) Check the following if needed:

Protection of Human Subjects Assurance/Certification/Declaration of Exemption (Formerly Optional Form – 310)

[Assurance/Certification Attachments](#)

OTHER REVIEW COMMITTEES

0 unresolved
comment(s)

If you check any of the below committees, additional materials may be required with your application submission.

Does your research fall under the purview of any of the other review committees listed below? [If yes, check all that apply and attach applicable materials using the attachment button at the bottom of your screen.]

Yes No

Additional Information	
 Institutional Biosafety Committee	
• Institutional Biosafety Committee (IBC) - Attach required IBC materials
 Radiation Safety Committee	
• Radiation Safety Committee (RSC) - For applicability, see instructions and attach form
 Radioactive Drug Research Committee	
• Radioactive Drug Research Committee (RDRC)
 Markey Cancer Center (MCC) Protocol Review and Monitoring Committee (PRMC)	
• Markey Cancer Center (MCC) Protocol Review and Monitoring Committee (PRMC)** - Attach MCC PRMC materials, if any, per instructions.
 Graduate Medical Education Committee (GME)	
• Office of Medical Education (OME)
 Office of Medical Education (OME)	
• Graduate Medical Education Committee (GME)

Attachments

**** If your study involves cancer research, be sure to select "Cancer Research" in the "Research Attributes" section.** ORI will send your research protocol to the Markey Cancer Center (MCC) Protocol Review and Monitoring Committee (PRMC). The MCC PRMC is responsible for determining whether the study meets the National Cancer Institute (NCI) definition of a clinical trial and for issuing documentation to you (the investigator) which confirms either that PRMC approval has been obtained or that PRMC review is not required. Your IRB application will be processed and reviewed independently from the PRMC review.

ADDITIONAL INFORMATION/MATERIALS

0 unresolved
comment(s)

Do you want specific information inserted into your approval letter? Yes No

Approval Letter Details:

If you wish to have specific language included in your approval letter (e.g., serial #, internal tracking identifier, etc...), type that language in the box below exactly as it should appear in the letter. The text you enter will automatically appear at the top of all approval letters, identical to how you typed it, until you update it. Don't include instructions or questions to ORI staff as those will appear in your approval letter. **If these details need to be changed for any reason, you are responsible for updating the content of this field.**

Additional Materials:

If you have other materials you would like to include for the IRB's consideration, check all that apply and attach the corresponding documents using the Attachments button below.

- Detailed protocol
- Dept. of Health & Human Services (DHHS) approved protocol (such as NIH sponsored Cooperative Group Clinical Trial)
- Other Documents

Protocol/Other Attachments

Attach Type	File Name
Protocol	CC-OD-21-1789.pdf
Protocol	RE_ IRB# 64473 TMS for Smoking Cessation in PLWHA.pdf

NOTE: Instructions for Dept. of Health & Human Services (DHHS)-approved protocol

If you have password protected documents, that feature should be disabled prior to uploading to ensure access for IRB review.

To view the materials currently attached to your application, click "All Attachments" on the left menu bar.

SIGNATURES (ASSURANCES)**0 unresolved
comment(s)**

Each Section/Subsection in the menu on the left must have a checkmark beside it (except this Submission section) indicating the Section/Subsection has been completed. Otherwise your submission for IRB review and approval cannot be sent to the Office of Research Integrity/IRB.

If applicable, remember to update the Approval Letter Details text box under the Additional Information section

If your materials require review at a convened IRB meeting which you will be asked to attend, it will be scheduled on the next available agenda and you will receive a message to notify you of the date.

If you are making a change to an attachment, you need to delete the attachment, upload a highlighted version that contains the changes (use Document Type of "Highlighted Changes"), and a version that contains the changes without any highlights (use the appropriate Document Type for the item(s)). Do **not** delete approved attachments that are still in use.

Principal Investigator's Assurance Statement

I understand the University of Kentucky's policies concerning research involving human subjects, and I attest to:

1. Having reviewed all the investigational data from this study, including a compilation of all internal and external unanticipated problems.
2. Having reviewed, if applicable, information from the sponsor including updated investigator brochures and data and safety monitoring board reports.

I also attest that I have reviewed pertinent materials concerning the research and concluded:

- The human subject risk/benefit relationship is unaffected, mitigated, or eliminated by closure of the study and all pertinent materials for closure of the research are being submitted to the IRB for consideration.

By checking this box, I am providing assurances for the applicable items listed above.

Your protocol has been submitted.

Attentional Bias Analyses. Attentional bias for cigarette cues will be calculated separately for each set of trials, by subtracting the average fixation time on neutral cues from the average fixation time on cigarette cues. Fixation time on cigarette cues for each session and resultant cigarette cue attentional bias score will be entered into separate linear fixed effects regression models. Dependent variables for these models will be fixation time on cigarette cues and attentional bias for cigarette cues respectively.

Cigarette craving analyses. TCQ-SF scores will be entered into a linear fixed effects regression model. Outcome variables for this model will be TCQ-SF score.

Resting state functional connectivity (rsFC) analyses. CONN functional connectivity toolbox (version 21.a) will be used for all preprocessing and neuroimaging analyses using standard procedures. Firstly, general linear model (GLM) analyses will explore if rsFC changed from two seeds (L. dIPFC and right insula) to all voxels following iTBS versus sham iTBS relative to baseline rsFC in participants who receive iTBS and sham iTBS. In first level analyses, a seed map will be created for every subject using respective seeds (L. dIPFC or right insula). In second level analyses, a between conditions contrast will be used to assess rsFC within-subject differences baseline, and following iTBS and sham ITBS. All second level analyses will use cluster level inferences based on Gaussian Random Field Theory. This will be done using general linear models (GLM) to generate a statistical map of t-values, that will subsequently threshold to reveal non overlapping clusters (<https://web.conn->

toolbox.org/fmri-methods/cluster-level-inferences). Two-sided p-values will be generated using cluster-level false discovery rate (FDR) correction ⁶².

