74. Alcorn JL, 3rd, Strickland JC, Lile JA, Stoops WV, Rush CR. Acute methylphenidate administration reduces cocaine-cue attentional bias. *Prog Neuropsychopharmacol Biol Psychiatry*. 2020;103:109974.

Objectives

List your research objectives. Please include a summary of intended research objectives in the box below.

Before the study proper, we will conduct a pilot study to validate our attentional bias task in healthy controls who may or may not have a history of current or active smoking. The specific aim of this pilot would be to show differences in attentional bias between smokers and non smokers.

Study proper. Specific Aim 1 will demonstrate whether one session of MRI targeted TBS to left dorsolateral prefrontal cortex (DLPFC) will decrease attentional bias to smoking cues, compared to sham TMS. Subjects will receive both one TBS session (1800 pulses) and one session of sham TMS, lasting 10 minutes on separate days. They will perform an attentional bias task before and after TBS. We hypothesize that TBS will significantly decrease post session attentional bias to smoking cues compared to sham TMS.

Specific Aim 2 will demonstrate whether one session of TBS versus sham TMS, to left DLPFC can modulate stress induced craving for smoking. Subjects will perform the short form of tobacco craving questionnaire (TCQ-SF) before and after TBS. We hypothesize TBS will significantly decrease craving in smoking patients compared to sham TMS.

Specific Aim 3 will demonstrate whether one session of TBS versus sham TMS, to left DLPFC can increase seed based functional connectivity (fc) in the ventral striatum. We will acquire resting state functional MRI (fMRI) scans before and after TBS in all subjects. We hypothesize increase in fc in the dorsal anterior cingulate – ventral striatum circuit after TBS.

Study Design

Describe and explain the study design (e.g., observational, secondary analysis, single/double blind, parallel, crossover, deception, etc.).

- **Clinical Research:** Indicate whether subjects will be randomized and whether subjects will receive any placebo.
- **Community-Based Participatory Research:** If you are conducting community-based participatory research (CBPR), describe strategies for involvement of community members in the design and implementation of the study, and dissemination of results from the study.

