We will measure attentional bias using a validated database of smoking and neutral cues and Tobii Pro Fusion 120 Hz eye tracker (Tobii Technology, Sweden). Smoking and neutral cues will be presented side-by-side on the screen for 1000?milliseconds. Eye tracking will record eye movements and fixation times for both cue types. Upon offset of the cues, a visual probe ('X') will appear on either the left or right side of the computer screen. Participants will be instructed to respond as quickly as possible to the probe. The primary dependent variable will be mean fixation time (milliseconds) calculated by summing the total fixation time for each cue type and then dividing by the total number of critical trials (i.e., 40). Reaction times to the visual probe will also be collected.

Attention bias behavioral activation (ABBA) task using go/no go

A modified cued go/no-go task is used as a measure of inhibitory control. The procedures and parameters for the attentional bias-behavioral activation (ABBA) task are identical to the traditional cued go/no-go task except that opiate-related images serve as go cues and neutral images serve as no-go cues. Opiate related images and neutral images that will be used for this task are attached below.

Delayed discounting task

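### Aim 1 is a hypothesis about attentional bias, but the named primary variable is fixation time per cue type, and the bias score is only one of two unranked outcomes

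*Combined protocol and SAP*

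**What the plan says.** Three parts of the combined protocol and SAP bear on how Aim 1 is decided.

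- **Objectives, Specific Aim 1.** One hypothesis is given: "TBS will significantly decrease post session attentional bias to smoking cues compared to sham TMS". The construct is bias.
- **Research Procedures, Attentional Bias task.** "The primary dependent variable will be mean fixation time (milliseconds"), computed separately for each cue type over 40 critical trials. Probe reaction time is also collected and is not called primary.
- **Attentional Bias Analyses** (statistical text at the end of the document). The bias score is formed "by subtracting the average fixation time on neutral cues from the average fixation time on cigarette cues". Cigarette-cue fixation time and the bias score then "will be entered into separate linear fixed effects regression models", and "Dependent variables for these models will be fixation time on cigarette cues and attentional bias for cigarette cues respectively".

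The analysis text gives Aim 1 no order of testing, significance level, sidedness or multiplicity rule. The only such statement concerns the connectivity analysis: "Two-sided p-values will be generated using cluster-level false discovery rate (FDR) correction".

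**The concern.** By the plan's own definition, cigarette-cue fixation time is not attentional bias. It is one term of a difference. It can fall because attention moves from cigarette to neutral cues, which is what Aim 1 is about. It can also fall because the subject looks less at either picture, which is not.

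The hypothesis points to the difference score. The task description points to fixation time by cue type. The analysis paragraph gives both cigarette-cue fixation and the difference score equal standing. A reader of the results could not tell from the plan which model settles Aim 1.

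Two things are at stake. The first is a modest increase in false positives from having two chances. The second is more serious: a conclusion about bias could rest on a measure that does not isolate bias.

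**Working it through.** The plan gives no alpha, effect size or power figure for Aim 1, so there is no stated number to reproduce.

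**Inputs from the documents**
- Two dependent variables, in separate models (Attentional Bias Analyses).
- 30 subjects, each receiving TBS and sham (Study Design).
- Bias = cigarette-cue minus neutral-cue fixation (Attentional Bias Analyses).

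**Assumptions**
- Two-sided 0.05 per test.
- C and N are the within-subject TBS-minus-sham contrasts in cigarette-cue and neutral-cue fixation, with equal variances and correlation r. The documents do not give r. The cues are shown side by side, so it may well be negative. I take -0.9 to 0.9.
- A paired comparison stands in for the regression model.

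**Step 1: correlation between the two outcomes.** Because the bias score contains C,

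corr(C, C - N) = (1 - r) / sqrt(2 - 2r) = sqrt((1 - r)/2).

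**Step 2: error when TBS affects neither variable.** Under a bivariate normal, the chance that at least one test is significant is as follows.

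| r | corr(C, C - N) | Any false difference | False decrease only |
|---|---|---|---|
| -0.9 | 0.975 | 6.0% | 3.0% |
| -0.5 | 0.866 | 7.3% | 3.7% |
| 0 | 0.707 | 8.3% | 4.2% |
| 0.5 | 0.500 | 9.1% | 4.5% |
| 0.9 | 0.224 | 9.6% | 4.8% |

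A single test gives 5% and 2.5%. At r = -1 the two tests coincide and give those same values. If the tests were independent, the figure for any difference would be 1 - 0.95² = 9.75%.

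**Step 3: a fall in looking that leaves bias unchanged.** Suppose TBS, relative to sham, lowers looking at both cue types equally. Then C - N has mean zero and the bias hypothesis is false. Let d be the drop in C in units of the SD of C. The paired t statistic has 29 degrees of freedom and noncentrality d × sqrt(30). The chance of a significant decrease in cigarette-cue fixation is below.

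| Assumed d | d × sqrt(30) | Significant fall in cigarette-cue fixation | Significant fall on either variable (simulated, r = -0.5 to 0.5) |
|---|---|---|---|
| 0.1 | 0.55 | 7.6% | 8-9% |
| 0.2 | 1.10 | 18% | 18-20% |
| 0.3 | 1.64 | 36% | 36% |
| 0.5 | 2.74 | 75% | 75% |

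Nearly all of the last column comes from the cigarette-cue test. Its rejections reflect a real fall in cigarette-cue fixation. The error lies in reading that fall as reduced bias. A multiplicity correction does not address this; the choice of variable does.

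**The case against.** The strongest reply is that the plan already limits what counts as bias. Aim 1 has one hypothesis, it is about bias, bias is defined as a difference, and the other outcome is labelled plainly as fixation time. On this reading the task description only ranks eye tracking above reaction time, and the bias score is derived from the two fixation means. Nothing in the plan says that a result on cigarette-cue fixation alone would be success on Aim 1. That is fair: such a claim is a possibility left open, not a stated intention. But no rule excludes it, and the one variable called primary is the raw measure.

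A reader might infer that the plan names no primary at all. The documents do not support that, because the task description names one. The fault is that it does not match the hypothesis.

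A reader might also infer that two tests alone push the chance of a false claim of reduced bias above 5%. The documents do not support that either. They state no level or sidedness for Aim 1, and with two-sided 0.05 tests the chance of a false decrease under no effect stays at 3.0-4.8%. The 6.0-9.6% figures include increases, which cannot support the hypothesis. One-sided 0.05 tests would give 5.9-9.4%, but the plan does not specify them.

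The sham comparison also removes any fatigue or repetition effect common to both sessions. Only a TBS-specific fall in looking would mislead, and its size is assumed here. Finally, the study describes itself as an exploratory pilot, which weakens the case for strict error control. It does not weaken the case for testing the variable that the hypothesis names.

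**Conclusion.** The point stands as a mismatch between the hypothesis, the named primary variable and the analysis outcomes. The multiplicity cost is modest: on the assumptions above, it at most nearly doubles the chance of a false decrease, which stays below 5%. The main exposure is a TBS-specific, cue-independent drop in looking. That would make cigarette-cue fixation significant in 7.6% to 75% of trials for assumed drops of 0.1 to 0.5 SD, with bias unchanged, and the plan has no rule to stop this being reported as a positive Aim 1. The documents do not show that such a drop will occur or how large it would be. For a pilot of 30 subjects this should be corrected, and it can be corrected in wording.

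**What to change.** In both the Attentional Bias task description and Attentional Bias Analyses, name the bias score (cigarette-cue minus neutral-cue fixation, TBS versus sham) as the single primary variable for Aim 1, and state its significance level and sidedness. Report cigarette-cue fixation, neutral-cue fixation and probe reaction time as supportive, with no separate claim of success. Showing the two fixation components beside the bias score lets a reader see whether a change reflects redirected attention or less looking overall.

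No new data or procedures are needed. The sponsor gives up the option of claiming Aim 1 on cigarette-cue fixation alone.

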A sequential timeline of assessments and interventions are shown in table one. After informed consent, subjects will get an MRI brain scan at the Magnetic Resonance Imaging and Spectroscopy Center (MRISC) affiliated with University of Kentucky. Subjects will also be escorted to the MRISC at the UK Medical Center by the PI ([name]) and a research assistant. Subsequently, neuroimaging data (MRI brain) will be acquired using a Siemens 3-Tesla (3T) PRISMA MRI scanner as described under Data Collection below. This will happen on day 1. Then, on days 2 and 3, subjects will be scheduled for three hour experimental sessions at the TMS Suite at [name]. During these three hour sessions, subjects will perform the tobacco craving questionnaire (TCQ) while performing stress induced craving paradigm, attentional bias task and delayed discounting task. These activities will last an hour. Then we will obtain active motor threshold (AMT) from the first dorsal interosseous (FDI) muscle and left motor cortex, following which we will administer either a session of theta burst stimulation (TBS) for 9 minutes at 80% active motor threshold (AMT) or sham TMS to the left dorsolateral prefrontal cortex using a figure 8 coil and MagVenture MagPro x100 device (MagVenture A/S, Denmark), with TMS coil position stabilized using BrainSight (Rogue Solutions, Montreal, Canada). We will record motor evoked potential before and after the TBS session to assess response (10% increase in MEP to be a cutoff parameter). These activities will last another hour. After the TBS/sham TMS session, subjects will perform TCQ concomitant with the stress induced craving paradigm, attentional bias and delayed discounting tasks. These will last an hour. Then subjects will be transported to MRISC for their post TBS session MRI brain scan in the 3-Tesla (3T) PRISMA scanner.

Table 1

Study Task Study Day Pre- TBS Post-TBS

Urine Pregnancy Test 1

MRI brain at MRISC (Pre-TBS) 1

Exhaled CO 2 and 3 X

Motor Threshold 2 and 3 X

Eye tracking to measure AB 2 and 3 X X

Delayed Discounting Task 2 and 3 X X

Tobacco Craving Questionnaire 2 and 3 X X

TMS Side Effects Questionnaire 2 and 3 X

Treatment Acceptability Questionnaire 2 and 3 X

MRI brain at MRISC (Post-TBS) 2 and 3 X

Attachments

Subject Recruitment Methods & Advertising

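### Connectivity is tested from two seeds with cluster-level FDR, but the plan does not state the FDR family, the q level or a primary seed; corrected map by map at an assumed q of 0.05, the iTBS-sham comparison carries a 5% to 9.75% chance of a false cluster.

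*Combined protocol and SAP*

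**What the plan says.** The relevant text is the paragraph on resting state functional connectivity (rsFC) analyses in the statistical analysis section at the end of the document.

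- **Seeds.** "general linear model (GLM) analyses will explore if rsFC changed from two seeds (L. dIPFC and right insula) to all voxels". First-level maps are made for each seed separately.
- **Comparison.** The change is assessed "following iTBS versus sham iTBS relative to baseline rsFC in participants who receive iTBS and sham iTBS". For the second level, "a between conditions contrast will be used to assess rsFC within-subject differences baseline, and following iTBS and sham ITBS".
- **Inference.** "All second level analyses will use cluster level inferences based on Gaussian Random Field Theory". A map of t-values is thresholded into clusters, and then "Two-sided p-values will be generated using cluster-level false discovery rate (FDR) correction".

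The paragraph gives no q level, alpha or cluster-forming threshold. It does not say whether FDR is controlled within one map or across both seeds, and it does not rank the seeds or list the contrasts to be read.

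Two other places matter. Table 1 under Study Design lists "MRI brain at MRISC (Pre-TBS) 1", that is, one pre-stimulation scan on day 1, with post-session scans on days 2 and 3. Specific Aim 3 under Objectives predicts increased connectivity in the dorsal anterior cingulate-ventral striatum circuit after TBS.

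**The concern.** Each seed produces its own whole-brain map, and each map can yield clusters. If FDR is applied to one map at a time, the plan has two separate chances to report a corrected iTBS effect and nothing that ties them together. When no effect exists anywhere, any declared cluster is false, so FDR at level q gives each map a probability of about q of a false finding. Two maps give up to nearly twice that.

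A cluster labelled FDR-corrected will usually be read as controlled evidence, and a reader of the report could not tell that the control stopped at the edge of one map. The Background section says that data from this study will support a grant resubmission. It does not single out connectivity, so the consequence is a matter of degree. With the family undefined, the choice could also be made after the maps have been seen.

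**Working it through.** The plan gives no error rate, FDR level or power figure for this analysis, so there is no figure of its own to reproduce.

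**Inputs**
- Seeds: 2 (rsFC analyses paragraph).
- Contrast per seed: 1, iTBS versus sham relative to baseline. Table 1 has a single shared baseline scan, so (iTBS − baseline) − (sham − baseline) = iTBS − sham.
- Conditions at the second level: 3, so 3 possible pairs. The text describes one contrast and does not list pairs.
- q: not stated. Assumed 0.05, with a range of 0.01 to 0.10.
- FDR family: not stated. Assumed to be one map.
- Planned n: 30, within subject (Study Design).

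**Step 1: one map.** Under a complete null, FDR at level q means P(any cluster declared) = q. This takes the cluster p-values as valid. That depends on the cluster-forming threshold, which is not given.

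**Step 2: two seed maps, iTBS versus sham.** For m independent maps corrected separately, P(any) = 1 − (1 − q)^m. With m = 2 and q = 0.05: 1 − 0.95² = 0.0975, or 9.75%. If the maps were identical, the value would be 5%. Both maps come from the same scans, so the truth lies between.

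A simulation used paired t-tests with Benjamini-Hochberg within each map, 1 to 200 independent units per map and n = 10 or 30. It gave roughly 8-11% for seed correlation up to 0.6 and 7-9% at 0.9.

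**Step 3: if all three condition pairs were also read.** With m = 6: 1 − 0.95⁶ = 26.5% if independent. Pairs that share a condition are correlated. Allowing for that, and for seed correlation from 0 to 0.9, the simulation gave about 18% to 27%.

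**Step 4: range over the unstated q (independent maps)**

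| q | 2 maps | 6 maps |
|---|---|---|
| 0.01 | 2.0% | 5.9% |
| 0.025 | 4.9% | 14.1% |
| 0.05 | 9.75% | 26.5% |
| 0.10 | 19.0% | 46.9% |

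**Step 5: after the fix, at q = 0.05.** One pooled FDR family gives about 5%. Using 0.025 per seed gives 1 − 0.975² = 4.9%. With a fixed order, a false cluster in the second seed can be declared only after one in the first, so P(any) = 5%.

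**Step 6: power cost, illustrative.** Take one scalar paired test with n = 30 and standardised difference 0.529. Power is 80% at 0.05 and 70% at 0.025. In a simulation of pooled FDR starting from 76% per seed, power fell to 74% when both seeds carried an effect and to 69% when only one did. These are not models of cluster inference; they show the order of the loss.

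**The case against.** **The analysis is exploratory, and FDR is a deliberate choice.** The paragraph says the analyses will explore, and FDR controls the share of false discoveries rather than the chance of any. Judging it by the chance of any false cluster is stricter than what was chosen, and the figures hold only under a complete null. This stands as a limit on severity. It does not remove the gap, because FDR is itself defined only once its family and level are stated. Specific Aim 3 is also worded as a demonstration, not an exploration.

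**Pooling may have been intended.** The text does not say that FDR stops at one map. A reader might infer that within-map correction is the stated plan; it is an inference from silence. It is the natural one, since the text goes from a map to its clusters to FDR and never mentions combining seeds.

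**The 5% level is not in the documents.** A reader might take it as planned. It is an assumption, hence the range.

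**A reader might infer an error rate of 23-26%, or up to five times nominal.** That needs three pairwise maps per seed, all read as findings. The plan names one iTBS-versus-sham comparison and then a single contrast over the three conditions, which could equally be an omnibus test. The documents do not clearly plan the six-map analysis.

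**A reader might call any chance cluster a false Aim 3 finding.** Aim 3 predicts an increase in one circuit. A chance cluster from a dlPFC or insula seed would not by itself meet that hypothesis. This objection stands, and it exposes a mismatch arguably more important than the multiplicity.

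**The power cost is for n = 30.** The continuing-review section reports a total of 10 enrolled. At n = 10 the same illustrative effect has 32% power at 0.05 and 21% at 0.025, so the loss would fall on an analysis already weak.

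**Conclusion.** The concern holds in a limited form. Two whole-brain seed maps are planned, and the plan leaves open the FDR family, q, the primary seed and the set of contrasts. Under within-map FDR, valid cluster p-values, a complete null and an assumed q of 0.05, the chance of at least one false cluster for iTBS versus sham is between 5% and 9.75%, against about 5% with one family. The higher figure of about 18-27% applies only if all three condition pairs are also read as findings.

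This is a specification gap that is cheap to close. It does not show that the planned comparison is invalid. Separately, the circuit in Specific Aim 3 and the seeds in the rsFC analyses do not match. Closing the multiplicity gap does not make these maps a test of the Aim 3 hypothesis.

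**What to change.** Amend the rsFC analyses paragraph to:

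1. State q and the cluster-forming threshold.
2. Name iTBS versus sham as the single inferential contrast.
3. Treat the clusters from both seed maps as one FDR family. Alternatively, test left dlPFC first and right insula only if the first shows a cluster.
4. Label every other contrast, including those against baseline, descriptive.
5. Reconcile the seeds with Specific Aim 3: either add an analysis of the dorsal anterior cingulate-ventral striatum circuit, or say that the dlPFC and insula maps do not test that hypothesis.

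If maps have already been examined, report how many and give the pooled result.

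**Cost.** Items 1 to 4 take a sentence or two and no new data. Halving q per seed costs power, illustratively from 80% to about 70% for one scalar paired test at n = 30; pooled FDR should cost no more than that. The fixed order costs the first seed nothing, but a real effect seen only from the right insula could not then be declared. Item 5 may need one further analysis of scans that are already planned.
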